Need for Behavioral Interventions to Prevent Relapse and Address Mental Health and Chronic Pain Among Patients Treated with MAT for OUD. MAT has been shown to reduce illicit opiate use and improve health outcomes for patients with OUD;[21-29] however, not all patients will benefit, as treatment retention rates are unacceptably low. Data suggests that retention may be more of a problem for patients treated with buprenorphine compared to methadone: a secondary analysis of clinical trials found that retention at 24 weeks was 46% among buprenorphine treated patients compared to 74% among methadone treated patients ($p < 0.01$).[30] Estimates of buprenorphine retention in real-world office-based settings show that approximately a half, or less, of patients who are initiated in treatment are still retained a year later.[31-34] Studies with Kaplan Meier data demonstrate a steep drop-off early in treatment with median retention ranges 3-9 months.[32, 35, 36] Clearly there is an

opportunity to intervene with patients initiating treatment with MAT to improve retention rates. The most common reason for patients to become disengaged and not be retained in care is relapse to substance use.[31] In addition, upon entering MAT, the majority (~52%) use multiple substances [37-40] and there is a high prevalence (34-57%) of co-morbid psychiatric disorders [38, 41-43] and social problems.[41, 44, 45] Post-traumatic stress disorder (PTSD) prevalence is 33-50% among patients in SUD treatment,[46] and elevated among those with opioid dependence.[47, 48]

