4.1 Inclusion Criteria

Candidates for participation must meet all of the following criteria to participate in the study. Participants must be: 1) diagnosed with OUD, 2) enrolled in a medication treatment program for opioid use disorder, 3) over 18 years old, 4) enrolled and is stable in program involving (to assure medication initiation/induction has occurred) involving (if on buprenorphine) at least 4 weeks of treatment (to assure medication initiation/induction has occurred) and Rx appointments are less frequent than once/week, and (if on methadone) at least 90 days in treatment with a minimum dose of 60mg, no missed dose evaluation appointments in past 30 days, and no more than 3 missed doses in 30 days, 5) willing to forego (non-study) manual (e.g., massage) and/or mind-body therapies (e.g., mindfulness meditation) for 3 months (baseline to post-test); 6) willing to sign release for access of electronic medical records; 7) fluent in English; 8) able to attend study sessions when offered.

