Secondary Outcomes For comparison of treatment arms on measures of secondary outcomes, we will have 80% power to detect a minimum difference of 0.4 SD. For comparison of medication-assisted treatment retention rates, we hypothesize that retention rates at 12 months will be 60% in the TAU arm and 77% in the MABT arm. The comparison of proportions will have power of 80% to detect this difference. Exploratory Aim: at 6 months after 20% attrition, we expect the total sample to be N = 264 (132 per group) and assume the ability to detect, at minimum, a 15% difference between MABT and TAU groups in proportion of abstinent days. Under these assumptions, the power at 12 months to detect a group difference comparing those using substances at 6 months (nonresponders) in control to those using substances (nonresponders) at 6 months in MABT groups (who have been offered additional sessions) is .65 for a 40% non-responder rate (n = 53 per group). While underpowered, this exploratory aim would provide a reasonable sample size to estimate power for future related research questions and allows us to look at the question of MABT dose and re-engagement for those needing additional treatment support within the primary analysis.

Missing Data: We will evaluate differences in baseline characteristics between participants lost to follow-up versus those who are not. Missing data patterns will also be evaluated including the frequency and percentage of those missing for each variable and the distribution of the number of variables missing. In addition, data collected to the point of lost to follow-up will be compared to the data of those who complete the study to examine possible missing data mechanisms, e.g., missing completely at random (MCAR), missing at random (MAR), or not missing at random (NMAR). Sensitivity analyses will be performed to assess the possible impact of the missing data on the study results. We will consider various methods for missing TLFB including multiple imputation and pattern mixture models.[105] Similar methods will be used for other drug use and opioid craving. We anticipate there should be no missing data for retention since patients who are lost to follow-up are discharged from the program, therefore “missingness” is part of the variable definition.

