Randomization: Randomization will be provided by the project statistician. Stratified randomization, by study site, baseline self-reported chronic pain, and gender, will be used to distribute participants evenly between the two treatment conditions at each facility and within each gender. Randomization will use a modified minimization method algorithm[96] based on an overall imbalance score which measures how far out of balance (within strata) the study is for a given set of random assignments to ensure approximately equal accrual into the two experimental arms and to facilitate concealment of treatment assignments.

Treatment Assignment Procedures

Research coordinators will use the randomization program developed by the project statistician to determine the treatment assignment group following baseline data collection. Participants will be informed of their assignment within one week of the initial appointment by the Research Coordinator. Prior MABT studies showed no loss due to randomization to treatment group, thus we do not expect randomization to precipitate significant attrition. The Research Coordinator at each facility will not be blind to condition and will inform participants of their treatment condition and MABT therapist.

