9.6 Data Analyses

Primary Analysis To test the primary hypotheses, generalized linear regression models for dependent data will be used to compare percent days abstinent from opioid use in the two study groups between baseline to 6 months for the R33 study aims, and baseline to 12 months for the R01 study aims. Sensitivity analyses will also explore modeling opioid use as percent days abstinent during the assessment periods using Generalized Estimating Equations (GEE) [106] with a logit link and an exchangeable correlation structure. We will fit difference within group correlations structures (unstructured, independent, exchangeable, autoregressive) seeking the correlation structure that combines the fewest parameters with the best measure of fit using Akaike information criterion (AIC) and Bayesian information criterion (BIC). The logarithm of the total number of days in the assessment period will be included as an offset variable to account for the time at risk of relapse. The same analysis will be done to examine percent days abstinent on other illicit drugs and alcohol.

Secondary Analyses Analyses of secondary outcomes (mental and physical health outcomes and opioid craving) will utilize GEE as described above. Longitudinal analyses will examine treatment by time interactions on each of the outcomes. Analyses of retention in medication-assisted treatment will be done using a test of proportions retained in MAT as well as the log-rank test to compare survival curves. A sensitivity analysis will use Cox regression to adjust for pre-treatment covariates. Last, we plan to include exploratory analyses to also examine treatment by gender interactions.

Exploratory Analysis Linear regression model using GEE will be used to explore the effect of additional MABT dose on days abstinent from opioid use and related health outcomes at 12 months among the MABT 6 month non-responders compared to control non-responders. Characteristics of responders will be compared to those of non-responders using t-tests, chi-square, or Fisher's exact tests.

In addition, we will explore the relationship with dose, within the MABT group. Dose response functions will be estimated thorough a regression approach treating the number of sessions as the continuous treatment variable. Such models are appropriate when the treatment intensity is endogenous (that is, selection into treatment depends on both observable and unobservable factors).

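### The retention tests name no strata although allocation is balanced within site, sex and chronic pain; stratifying by site is a small, free improvement

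*Combined protocol and SAP*

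**What the plan says.** Retention is tested "using a test of proportions retained in MAT as well as the log-rank test to compare survival curves" (section 9.6, Secondary Analyses). No stratification factor is attached to either test. Adjustment appears once, in the next sentence: "A sensitivity analysis will use Cox regression to adjust for pre-treatment covariates". The covariates are not listed.

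On allocation, section 9.2 states: "Stratified randomization, by study site, baseline self-reported chronic pain, and gender, will be used". Sections 3, 4.3 and 6.2.2 describe the same scheme, a modified minimization that works within strata.

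On the sites, the Version 4.0 summary of revisions records that one added site is a methadone clinic and that the others prescribe buprenorphine. Section 4.1 sets entry at four weeks or more of treatment for buprenorphine, while the methadone rule reads "if on methadone) at least 90 days in treatment with a minimum dose of 60mg" and adds attendance conditions.

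Two statements bear on whether site predicts retention. Section 2.1 reports, from a secondary analysis of other trials, that "retention at 24 weeks was 46% among buprenorphine treated patients compared to 74% among methadone treated patients". Section 5.2 describes the outpatient programmes at the study sites as comparable.

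On power, section 9.2 says "we hypothesize that retention rates at 12 months will be 60% in the TAU arm and 77% in the MABT arm" and then "The comparison of proportions will have power of 80% to detect this difference".

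**The concern.** When arms are balanced within a factor that predicts the outcome, the between-stratum part of the outcome variance cannot contribute to the difference between arms. A pooled test still counts that part in its standard error. The result is a test below its nominal level, a confidence interval that is slightly too wide, and some lost power. A test stratified by the same factor recovers this.

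There is reason to expect site to matter here. One site uses a different medication, the cited retention figures differ by medication, and the two site types admit patients at different points after treatment start, when section 2.1 says discharge is concentrated early. Section 9.1 still lists only the three earlier sites, so the statistical section does not appear to have been revisited for the new mix. Retention is one of the two outcomes in Secondary Objective 2. Because the strata and covariates are unstated, they could also be chosen after the data are seen.

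**Working it through.** **1. The plan's own figure.** Inputs: 60% versus 77% and 80% power (section 9.2); 165 per arm, or 132 after the 20% attrition in section 9.2. Two-sided 5% is stated for the primary outcome and assumed here for retention.

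Power = Φ{[√n·d − 1.96·√(2p̄(1−p̄))] / √(p₁(1−p₁)+p₂(1−p₂))}, with d = 0.17 and p̄ = 0.685.

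- 132 per arm: (1.953 − 1.288)/0.646 = 1.03, so 84.9%. With the Fleiss continuity correction, 81.5%.
- 165 per arm: (2.184 − 1.288)/0.646 = 1.39, so 91.7% (89.7% corrected).
- Log-rank: hazard ratio = ln 0.77 / ln 0.60 = 0.512. Expected events at 132 per arm are 132 × (0.40 + 0.23) = 83, giving 86.3% by Schoenfeld's formula.

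The stated 80% is therefore reproduced at 132 per arm with the correction. Section 9.2 expects no missing retention data, so 165 per arm is also a fair denominator.

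**2. Level of the pooled proportion test, by formula.** Let f be the methadone share, g the gap in retention between site types and p the overall retention. The share of outcome variance lying between site types is R² = f(1−f)g² / [p(1−p)]. With exact balance, the true level is about 2[1 − Φ(1.96/√(1−R²))].

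The documents do not give f; 10 to 50% is assumed. The gap g = 0.74 − 0.46 = 0.28 is borrowed from section 2.1, and 0.15 is an assumed smaller value. Overall TAU retention is held at p = 0.60.

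- f = 0.10, g = 0.28: R² = 0.09 × 0.0784/0.24 = 0.029; level 4.7%.
- f = 0.33, g = 0.28: R² = 0.2211 × 0.0784/0.24 = 0.072; level 4.2%.
- f = 0.50, g = 0.28: R² = 0.25 × 0.0784/0.24 = 0.082; level 4.1%.
- f = 0.33, g = 0.15: R² = 0.2211 × 0.0225/0.24 = 0.021; level 4.8%.

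**3. Simulation of all four tests.** Exponential discharge times, follow-up to 12 months, 1:1 balance within site × sex × pain (alternating assignment within strata, approximating the minimization), and no effect of sex or pain on retention. Level: 330 participants, 25,000 runs. Power: a common hazard ratio of 0.50 to 0.51 giving 77% overall in MABT, 12,000 runs. Monte Carlo error is about 0.14 points for level and 0.3 points for power. Each cell shows pooled, then stratified by site, in %.

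| Methadone share | Gap (points) | Level, proportions | Level, log-rank | Power, proportions, 132/arm | Power, log-rank, 132/arm |
|---|---|---|---|---|---|
| 10% | 28 | 4.5, 4.8 | 4.5, 4.8 | 85.1, 85.6 | 85.6, 85.9 |
| 20% | 28 | 4.4, 5.0 | 4.4, 5.1 | 85.5, 86.4 | 86.0, 86.9 |
| 33% | 28 | 4.3, 5.1 | 4.3, 5.1 | 85.7, 86.9 | 86.2, 87.5 |
| 50% | 28 | 4.0, 4.9 | 4.2, 5.1 | 85.8, 87.4 | 86.5, 88.3 |
| 33% | 15 | 4.9, 5.1 | 4.8, 5.1 | 84.8, 85.1 | 85.1, 85.3 |

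With the 28-point gap, stratifying gains about 0.2 to 1.8 points at 132 per arm and 0.3 to 1.0 at 165 per arm. With the 15-point gap it gains at most about 0.4 points in these runs. For a smaller, assumed treatment effect of 13 points at 165 per arm, the largest gain seen was about 2.5 points (69.6% to 72.1%, log-rank).

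**The case against.** The other side has four good arguments. First, pooled testing is inferred from silence, and the planned Cox model may already include site, sex and pain. Second, no retention is reported for any study site. The 46% and 74% are by drug, at 24 weeks and from outside trials, whereas this trial enrols patients already established in treatment, after the early losses that section 2.1 describes. Third, section 5.2 calls the programmes comparable. Fourth, the error is conservative, so it cannot manufacture a claim of benefit.

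All four limit the size of the point, and they stand to that extent. They do not remove it. An unlisted covariate set in a sensitivity analysis does not commit the main tests to anything. The care detailed in section 5.2 is largely buprenorphine care, so the word comparable does not settle how a methadone clinic retains patients.

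A reader might go further and infer that retention is known to differ strongly by site type and that the pooled tests waste much power. Simulations with a hazard ratio of 0.65 and assumed site retention of 50% and 85%, or spread from 35 to 85%, do show log-rank losses of about 4.6 to 6.5 points (56.1% against 60.7%; 55.7% against 62.2%). None of those inputs is in the documents, and the plan's own effect implies a hazard ratio near 0.51. Nor do the documents quantify any difference in retention by sex or chronic pain; the preface says only that pain may contribute to treatment failure.

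**Conclusion.** The point holds as a minor one. Section 9.6 does not carry the allocation factors into the retention tests, and site is likely, though not shown, to predict retention. If a 28-point gap held between site types, the pooled tests would run at about 4.0 to 4.5% (4.1 to 4.7% by the formula for proportions) and lose about 0.2 to 1.8 points of power at 60% versus 77% with 132 per arm. With a 15-point gap the loss is under 1 point.

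These sizes rest on an assumed methadone share of 10 to 50%, a gap borrowed from outside trials, and no effect of sex or pain. It would be wrong to conclude that the stated 80% power is at risk: the pooled tests keep about 85% or more in every scenario run at the plan's own rates. The case for change is that stratifying gives better calibrated tests and intervals and slightly more power at no cost, and fixes the choice in advance.

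**What to change.** In section 9.6:

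- Specify a log-rank test stratified by site, and a Cochran-Mantel-Haenszel comparison of 12-month retention stratified by site, reported with the risk difference and its confidence interval.
- Stratify the Cox model by site and name sex and baseline chronic pain as its covariates.
- Keep the unstratified tests as sensitivity analyses.

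Do not add time in treatment at randomization as a covariate unless it is already recorded. The record extraction described for retention is the discharge date, and no listed measure captures time in treatment.

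The cost is a few sentences in the plan and a few lines of code. Site, sex and chronic pain are already recorded for allocation, so no new data are needed.

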MABT Reduces Psychological Symptoms and Improves Emotional Well-being, Mindfulness, and Interoceptive Skills: MABT SUD treatment research (R21 study) showed promising results with significant between-group differences with moderate to large effects on mental health outcomes between MABT+TAU compared to TAU at 9 months. These included depression symptoms, eating disorder symptoms, perceived stress, dissociation, and physical symptom frequency.[85] The R01 pre-post findings (N = 187) showed significant improvements for MABT compared to TAU in craving, depression among those that received the full intervention dose, improved emotion regulation (self-report and psychophysiology), interoceptive awareness, and mindfulness skills among the MABT completers.[89]. Longitudinal outcomes showed maintained improvements for MABT vs. TAU on craving, psychophysiology (well-being/regulation), interoceptive awareness and mindfulness skills.[90] The proposed study examines many of the same mental health and process variables as in the above studies.

Patients on MAT frequently suffer from chronic pain, which is a risk factor for opiate craving

and potential relapse. We conducted a cross-sectional study (K23DA027367) of 106 adults who were maintained on buprenorphine or methadone.[91] The primary outcome was cold pain tolerance assessed by cold-pressor test. Chronic pain was highly prevalent (67%), and current pain was even moreso (83%). These results reinforced that pain and hyperalgesia are common problems in this population of persons who were maintained on MAT for treatment of OUD. In a subsequent study performing secondary analysis on data from the same sample, we examined relationships between pain and opioid craving and opioid use as measured by urine drug testing (UDT).[92] We found that 51% reported craving opioids in the past week, and 16% had a positive UDT for opiates. We concluded that chronic pain with associated opioid craving potentially places this population at risk for relapse. Results from these two studies underscore that there is an unmet need for interventions to address pain among persons on MAT in order to prevent relapse and improve addiction treatment outcomes.

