Massage/Body Literacy (40)	Massage/Body Literacy (10)	Massage/ Body Literacy (10)
	Interoceptive Training (30)	Mindful Body Awareness (30)
Session Review (15)	Session Review (15)	Session Review (15)
Homework	Homework	Homework

The MABT intervention is designed to increase self-awareness and thus participants sometimes experience discomfort, emotions, as well as insight. Overall MABT is very low risk, as the protocol is designed to be individualized to ensure safety and comfort of the participant. To date, here have been no serious adverse events associated with any MABT study.

For participants initially assigned to MABT who report continued use of opiates or other substances at 6 months, an additional 6 MABT sessions will be offered.

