Physical symptoms will be assessed using the Medical Symptoms Checklist (MSC) and pain severity and interference using the Brief Pain Inventory (BPI). The MSC measures the frequency (0-8 scale) and severity (0-10 scale) of 29 common physical symptoms.[19] The BPI is a validated, widely used measurement tool for assessing clinical pain. In the U.S. it has been validated in non-cancer patients with pain[18] and HIV-infected patients.[100] The assessment includes 13 questions which provide information on pain severity and pain interference in the past week. Participants are initially asked if they have experienced any significant pain in the past week, and if they respond positively they answer subsequent

questions about duration of pain, pain severity and interference. Pain severity is rated from 0 (“no pain”) to 10 (“worst pain imaginable”), and participants are asked to rate their current pain as well as pain at its worst, at its best, and on average in the past week. Pain interference includes information on the impact of pain on general activity, walking, work, mood, enjoyment of life, relations with others, and sleep, asking the participant to rate interference on a scale from 0 (“does not interfere”) to 10 (“completely interferes”), and is reported as the mean of seven questions. Participants who responded that they had no pain in the past week will be coded “0” for pain severity and interference. The BPI will be supplemented with a single question on duration of currently reported pain in order to establish whether the pain is acute or chronic.

Opioid craving will be assessed using a single item numeric scale.[5] Participants are asked: “On a scale of 0-10, please indicate how much craving you have experienced during the past week,” with responses anchored at “0=no craving at all” and “10-strongest craving ever”. Retention will be defined as days retained in the program, or time to program discharge. Program discharges are documented in the electronic medical record (EMR) and date of discharge will be extracted from the record.

R01-Specific Objective 3 Outcomes: Exploration of the effectiveness of additional MABT dose offered at 6 months to those with continued substance use compared to those with continued substance use at 6 months in the TAU will be assessed using the Time-Line Follow-Back Interview (TLFB)[3, 4] self-reported substance use as described in in the primary objective.

For description of the intervention, see Section 2.2.

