6.2.4 Follow-up Visits

Treatment

Initial Treatment Visit 1 (W1)

- Adverse Events
- MABT Process Evaluation (self-report by interventionists)

Initial Treatment Visit 2-8 (W2 - 11)

- Adverse Events
- MABT Process Evaluation (self-report by interventionists)
- MABT Practice Log (self-reported home practice by participants for use by interventionists)

Additional MABT Sessions 1-6 (W25 - W38)

- Adverse Events
- MABT Process Evaluation (self-report by interventionists)
- MABT Practice Log (self-reported home practice by participants for use by interventionists)

Assessments

Followup1-4 Assessment Visits (W12, W24, W39)

The follow-up assessments will be scheduled 12 weeks, 24 weeks, and 39 weeks from baseline, and takes approximately 45 minutes to complete. Coordinators will make every effort to schedule the assessment near to the target date, but are allowed -2 weeks/+4 weeks to capture follow-up assessment data. In addition to this assessment, we will also gather treatment retention data through electronic medical record (EMR) at the 6 and 12 month assessments.

Should a participant be unable to provide data during the scheduled assessment (e.g., unable to provide a urine sample, or unable to complete the assessment in one sitting), research coordinators have up to 14 days to complete the data collection for the assessment.

W24: The Time-Line Follow-Back Interview (TLFB)[3, 4] results collected at 6 months will be used to determine those in the MABT study group with continued substance use who will be offered six additional MABT sessions between month 6 and 9. Criteria for eligibility for additional MABT sessions is 1) randomized to the MABT + TAU study group, and b) self-report of substance use on the TLFB, including any days of heavy alcohol drinking and excluding marijuana use.

Primary outcome:

- Time-Line Follow-Back Interview (TLFB)[3, 4] will be used to assess self-reported opioid use, and use of other illicit drugs, marijuana, and alcohol.

Secondary outcomes:

- The PHQ-9 will be used to measure depression symptoms.[6, 7].
- The GAD-7 will be used to measure anxiety symptoms.[8]
- Posttraumatic Stress Disorder Checklist for DSM-5 (PCL-5),[9] assesses symptoms of post-traumatic stress on a Likert-type scale.
- Difficulty in Emotion Regulation Scale - short form (DERS- SF)[10] assesses difficulties in the modulation of emotional arousal.

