Secondary Objective 3 Hypothesis: Among participants in both groups who are using substances at 6 months, those in MABT group who receive additional MABT sessions (between 6-9 months) will show improved substance use at 12 months compared to those in TAU.

Exploration of the effectiveness of additional MABT dose offered at 6 months to those with continued substance use compared to those with continued substance use at 6 months in the TAU will be assessed using the Time-Line Follow-Back Interview (TLFB)[3, 4] self-reported as described in in the primary objective.

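### The 6-month non-responder rule counts any non-cannabis substance, but the exploratory analysis in 9.6 names opioid abstinence as its only substance-use outcome

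*Combined protocol and SAP*

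**What the plan says.** **Who enters the comparison.** Section 6.2.4 offers extra sessions to MABT participants on "self-report of substance use on the TLFB, including any days of heavy alcohol drinking and excluding marijuana use". Section 2.2 describes the same people as those who "report continued use of opiates or other substances at 6 months". Section 9.1, Secondary Objective 3, sets the comparison group as "Among participants in both groups who are using substances at 6 months".

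**What is hypothesised.** Sections 1.2 and 9.1 say that those who receive the added sessions "will show improved substance use at 12 months compared to those in TAU". Section 3 gives the measure for this objective as TLFB "self-reported substance use as described in in the primary objective". The primary objective in 1.1 covers opioids and other illicit substances, and section 3 counts heavy drinking days in its definition of other substance use.

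**What is analysed.** The Exploratory Analysis paragraph of 9.6 names "days abstinent from opioid use and related health outcomes at 12 months among the MABT 6 month non-responders", compared with control non-responders. It names no outcome for non-opioid drugs or heavy drinking and does not define the related health outcomes. The sentence in 9.6 on other illicit drugs and alcohol closes the Primary Analysis paragraph.

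**What power is stated.** Section 9.2 gives .65 for a 15-point difference in the proportion of abstinent days, with 53 per group. It does not say abstinent from what, and it calls the aim underpowered.

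**The concern.** Selection is on one quantity and the analysis is on a narrower one. Someone selected for stimulant use or heavy drinking, with no opioid days, enters with nothing to gain on opioid abstinence relative to their own 6-month value. If the added sessions reduced the stimulant use or drinking that led to them, the named substance-use outcome would not show it.

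Two things are at stake. An analyst who follows 9.6 literally would report an outcome narrower than the Objective 3 hypothesis. And 9.2 justifies this underpowered aim partly as a basis for sizing later studies. A difference averaged over people who cannot rise on the outcome may be too small for that purpose.

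**Working it through.** **Inputs**
- N after 20% attrition: 330 × .80 = 264, or 132 per arm (9.2).
- Non-responders: 132 × .40 = 52.8, taken as 53 per arm (9.2).
- Difference: 15 points (9.2).
- Alpha: .05 two-sided, stated in 9.2 for the primary aim and assumed here.
- TAU proportion: .80, the prior study's whole TAU arm (9.2). The plan does not restate it for this aim; it is inferred because it reproduces the stated power.
- f, the share of non-responders with opioid use at 6 months: not given, so shown as a range.

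**Step 1: reproduce .65.** For two proportions with pooled variance under the null,

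power = Φ{(|p2 − p1| − 1.96·√[2p̄(1 − p̄)/n]) / √[(p1(1 − p1) + p2(1 − p2))/n]}.

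With p1 = .80, p2 = .95, p̄ = .875 and n = 53, the null standard error is √(.21875/53) = .0642 and the alternative is √(.2075/53) = .0626. Power = Φ[(.15 − .1259)/.0626] = Φ(.385) = .65, as stated.

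**Step 2: dilute.** Suppose a share f uses opioids, with abstinent proportions of .80 and .95, and the other 1 − f stays at 100% in both arms. The arm proportions become 1 − .20f and 1 − .05f, a difference of .15f.

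| f | At 100%, per arm | TAU vs MABT | Difference (points) | Power, n = 53 |
|---|---|---|---|---|
| 1.0 | 0 | .80 vs .95 | 15 | .65 |
| .8 | about 11 | .84 vs .96 | 12 | .54 |
| .6 | about 21 | .88 vs .97 | 9 | .42 |
| .5 | about 26 | .90 vs .975 | 7.5 | .36 |
| .4 | about 32 | .92 vs .98 | 6 | .29 |

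Check at f = .4: p̄ = .95, the standard errors are .0423 and .0419, and Φ[(.06 − .0830)/.0419] = Φ(−.55) = .29.

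**Step 3: is restriction to opioid users a remedy?** It restores the 15 points but cuts n to 53f. Power is .55 (n about 42), .44 (about 32), .38 (about 26) and .31 (about 21) for f = .8, .6, .5 and .4. That is little better, and it drops the people selected on other substances.

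**Sensitivity.** The levels depend on the variance model. If abstinent days are treated as continuous with a fixed SD of .329 (the value at which 15 points and 53 per arm give .65), the four diluted figures are .47, .29, .22 and .15.

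**The case against.** The strongest reply is that the wider outcome is already in the plan. Sections 1.2, 3 and 9.1 state Objective 3 in terms of substance use, and 9.6 is only worded more narrowly. That is fair as far as it goes: the fault is a conflict between sections, not an aim without a suitable outcome. But 9.6 is where the analysis is specified. Its sentence on other drugs and alcohol belongs to the whole-sample primary analysis, and the undefined health outcomes cannot be assumed to include substance use, which the plan lists separately from mental and physical health. A reader might infer that 9.6 looks at nothing but opioids; because it also names those health outcomes, that goes too far.

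Second, participants at 100% are not uninformative. They can relapse to opioids by 12 months, and if relapse differs by arm they add to the difference. An opioid effect among all non-responders is also a legitimate quantity that matches the trial's primary outcome. Both points stand. The table assumes no such relapse, and the estimate should be called possibly diluted, not biased toward zero.

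Third, a reader might take the section 2.2 finding that "16% had a positive UDT for opiates", divide by the 40% non-response rate, and conclude that f = .16/.40 = .40, so that most non-responders (53 × .60, about 32 per arm) have no opioid use. The documents do not support this. The 16% is a single urine test in a separate cross-sectional sample of 106, while the TLFB covers about 90 days and would be expected to find more use. Table 3 in section 4 gives 70% past-30-day opioid use in the programme that the trial expects to resemble. Neither figure is f.

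Nor should a 6-point difference be set against a TAU value of .80 (.80 vs .86, power .13). With 60% at 100%, that would put opioid users at 1 − .20/.40 = .50, not the .80 that reproduces the plan's figure.

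**Conclusion.** The mismatch holds on the text alone. Entry is on any non-cannabis substance including heavy drinking, the hypothesis is about substance use, and the only substance-use outcome named for the analysis is opioid abstinence. As written, 9.6 would miss a benefit on the substance that led to the added sessions whenever that substance was not an opioid.

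The size cannot be fixed from the documents because f is unknown. Under the plan's apparent power method, and assuming that those without opioid use stay at 100% in both arms, power is about .54 to .29 for f from .8 to .4, against the stated .65. Whether many or few non-responders start at 100% is not known. The consequence is limited: the aim is exploratory, the plan already says it is underpowered, and no confirmatory conclusion rests on it.

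**What to change.** In the Exploratory Analysis paragraph of 9.6:
- Name percent days abstinent from any substance on the 6.2.4 list (opioids, other illicit drugs and heavy drinking, with cannabis excluded), in the assessment window ending at 12 months, as the Objective 3 outcome.
- Keep percent days abstinent from opioids as a second outcome.
- State that the 6.2.4 substance-use definition of non-response applies to both arms. Section 9.1 implies this, but 6.2.4 spells out the criteria only for MABT participants.

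In 9.2, say which abstinence measure and TAU value lie behind the .65. It carries over to the wider outcome only if the 15-point difference and the .80 are meant for that outcome.

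The cost is about one sentence in 9.6 and a clause in 9.2. The TLFB already collects the data at 24 and 52 weeks, and the rule for offering sessions is left as it is.
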